#### 4.2 Radiostereometric Analysis (RSA)

Radiostereometric Analysis is an accurate method of determining the migration of orthopaedic implants following surgical procedures such as total hip arthroplasties. RSA is able to measure early micromotion of the hip implant which is predictive of long-term fixation.

There are no RSA evaluations of the PINNACLE® Dual Mobility Metal Liner. Therefore, in order to evaluate future dual mobility hip replacement products, baseline migration values for the PINNACLE® Dual Mobility Implant will be determined; in addition, PINNACLE® Dual Mobility RSA data will allow for comparison with historical RSA data obtained using standard PINNACLE® acetabular constructs in study DSJ\_2018\_02.

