#### 8.2 Operative (Day 0)

Each Subject will receive a DePuy femoral stem with a polished neck in combination with a DePuy PINNACLE® acetabular cup. All Subjects will receive a PINNACLE® DM metal liner and a BI-MENTUMTM ALTRX® Dual Mobility Polyethylene Liner. Either metal or ceramic heads may be used; however, compatibilities must align with product labeling. Please note since revisions of existing THAs are acceptable to enroll into this study, variations in what is implanted will occur, however Subjects must receive the PINNACLE® DM metal liner and a BI-MENTUMTM ALTRX® Dual Mobility Polyethylene Liner. If the surgeon determines intraoperatively that there exists insufficient bone quality to support the implantation of the construct that Subject will be withdrawn from the study. Subjects that are withdrawn pre-operatively or intra-operatively will be replaced in order to have a minimum of 30 and up to 45 Subjects implanted with the study devices.

Each surgeon shall perform the surgical approach they are most comfortable with and have the greatest expertise.

Implant sizing shall be performed as per the surgeon's discretion for each individual Subject and will not be standardized between sites. Approximately 5-10 tantalum beads will be placed into the

4 MAR 2022; Version Rev 3 DSJ-2019-02 Confidential Page **20** of **47** TV-eFRM-02920 acetabulum. Bead placement will be standardized across study sites to reduce the possibility of unuseable RSA exams resulting from poor bead spacing or bead occlusion.

Any intra-operative adverse events will be captured as well as details of the surgery and implants/components used. The information collected from the 'Operative' time-point will be populated on the appropriate eCRFs as indicated in the Time and Events Table (Section 3.2).

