#### 8.7 Radiostereometric Analysis (RSA)

The RSA analysis will be the responsibility of the Canadian RSA Network. In summary, model based RSA software (RSAcore, Leiden, Netherlands) will be used for analysis, employing computer-models of the DePuy Synthes implants and inserted beads representing the bone rigid body. A central analysis service will be employed to analyze anonymized radiographs in a standard manner. DePuy Synthes will provide production CAD models as required for this analysis.

Three-dimensional migration measurements will be made of the acetabular shell relative to the bone beads. The 6-week examination will be used as reference against which the 3-month, 6-month, 1-year and 2-year post-operative exams will be compared. Results obtained from the model based RSA software will be changes from the 6-week (baseline) examination and will report the following at 3 months, 6 months, 1 year and 2 years:

- X, Y and Z translation measurements in mm from baseline;
- X, Y and Z rotation measurements in degrees from baseline;
- Maximal total point motion (one measurement in mm of maximal migration).

In a subgroup of Subjects, a second baseline will be defined as the result collected prior to discharge. For these Subjects, the translation, rotation and maximal total point motion will be reported at 6 weeks, 3 months, 6 months, 1 year and 2 years. This sub-analysis will determine the approximate magnitude of migration that occurs between the time of surgery and 6-weeks post-operative. Three-dimensional migration of the PINNACLE® Acetabular Shell shall be determined from the software.

Linear head penetration (in mm) will be performed by examining the change in distance between the center of the femoral head and the center of the acetabular shell between the 6-week (baseline) exam and the 1 year and 2 year exams. The femoral head center is determined by fitting a CAD sphere to the articular region of the femoral head (ignoring the trunnion area). The acetabular shell center is determined in a similar manner but also uses the silhouette of the cup face to determine its' center point.

4 MAR 2022; Version Rev 3 DSJ-2019-02 Confidential

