#### 11.12.4 Comparisons to Historical PINNACLE® Data

All primary, secondary, and exploratory endpoints will be compared to their counterparts in the DSJ\_2018\_02 (PINNACLE® RSA) study for the visits at which those endpoints are assessed using the t-test if the endpoint is continuous or Fisher's exact if the endpoint is categorical. The mean difference (PINNACLE® – PINNACLE® DM), the 2-sided 95% confidence interval for the difference, and the p-value for the test of equality will be presented. There are no formal hypotheses associated with those tests and the p-values and confidence intervals are only presented to facilitate clinical judgment.

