#### **PINNACLE Primary Cups**

		100 Series		Sector		Multihole		300	
	POROCOAT	GRIPTION	DUOFIX	POROCOAT	GRIPTION	DUOFIX	POROCOAT	GRIPTION	POROCOAT
48 mm	1217-01-048	1217-31-048	1217-11-048	1217-22-048	1217-32-048	1217-12-048	1217-20-048	1217-30-048	1217-03-048
50 mm	1217-01-050	1217-31-050	1217-11-050	1217-22-050	1217-32-050	1217-12-050	1217-20-050	1217-30-050	1217-03-050
52 mm	1217-01-052	1217-31-052	1217-11-052	1217-22-052	1217-32-052	1217-12-052	1217-20-052	1217-30-052	1217-03-052
54 mm	1217-01-054	1217-31-054	1217-11-054	1217-22-054	1217-32-054	1217-12-054	1217-20-054	1217-30-054	1217-03-054
56 mm	1217-01-056	1217-31-056	1217-11-056	1217-22-056	1217-32-056	1217-12-056	1217-20-056	1217-30-056	1217-03-056
58 mm	1217-01-058	1217-31-058	1217-11-058	1217-22-058	1217-32-058	1217-12-058	1217-20-058	1217-30-058	1217-03-058
60 mm	1217-01-060	1217-31-060	1217-11-060	1217-22-060	1217-32-060	1217-12-060	1217-20-060	1217-30-060	1217-03-060
62 mm	1217-01-062	1217-31-062	1217-11-062	1217-22-062	1217-32-062	1217-12-062	1217-20-062	1217-30-062	1217-03-062
64 mm	1217-01-064	1217-31-064	1217-11-064	1217-22-064	1217-32-064	1217-12-064	1217-20-064	1217-30-064	1217-03-064
66 mm	1217-01-066	1217-31-066	1217-11-066	1217-22-066	1217-32-066	1217-12-066	1217-20-066	1217-30-066	1217-03-066

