## PINNACLE Revision Cups

	Standard Profile	Deep Profile DPX
	GRIPTION	GRIPTION
54 mm	1217-16-054	1217-17-054
56 mm	1217-16-056	1217-17-056
58 mm	1217-16-058	1217-17-058
60 mm	1217-16-060	1217-17-060
62 mm	1217-16-062	1217-17-062
64 mm	1217-16-064	1217-17-064
66 mm	1217-16-066	1217-17-066
68 mm	1217-16-068	1217-17-068
70 mm	1217-16-070	1217-17-070
72 mm	1217-16-072	1217-17-072

4 MAR 2022; Version Rev 3 DSJ-2019-02 Confidential Page 45 of 47

Compatible femoral heads	Description			Finished
-	Brand	Diameter	Head Offset	Good Number
Std ARTICUL/EZE FEMORAL HEAD 12/14 TAPER	ARTICULEZE	22.225mm	[contact]
	ARTICULEZE	22.225mm	[contact]
	ARTICULEZE	28mm	[contact]
	ARTICULEZE	28mm	[contact]
	ARTICULEZE	28mm	[contact]
	ARTICULEZE	28mm	[contact]
M-Spec ARTICUL/EZE MOM FEMORAL HEAD 12/14 TAPER	ARTICULEZE M	28mm	[contact]
	ARTICULEZE M	28mm	[contact]
	ARTICULEZE M	28mm	[contact]
BIOLOX DELTA CERAMIC FEMORAL HEAD 12/14 TAPER	DELTA CERAMIC	28mm	[contact]
	DELTA CERAMIC	28mm	[contact]
	DELTA CERAMIC	28mm	[contact]
BIOLOX DELTA TS CERAMIC FEMORAL HEAD REVISION 12/14	DELTA TS CERAMIC	28mm	[contact]
	DELTA TS CERAMIC	28mm	[contact]
	DELTA TS CERAMIC	28mm	[contact]
BIOLOX forte (Alumina) ARTICUL/EZE CER BALL	ARTICULEZE CERAMIC	28mm	[contact]
	ARTICULEZE CERAMIC	28mm	[contact]

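### The historical comparison of shell migration ignores shell surface, so if the shell mix differs between the two studies the plan has no analysis that would show it

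*Combined protocol and SAP*

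**What the plan says.** Section 8.7 defines what is measured: "Three-dimensional migration measurements will be made of the acetabular shell relative to the bone beads". Section 4.2 gives the purpose of the outside reference as "comparison with historical RSA data obtained using standard PINNACLE" constructs, from DSJ_2018_02.

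Section 11.12.4 compares all primary, secondary and exploratory endpoints with that study, by t-test if continuous and Fisher's exact test if categorical. The output is "The mean difference (PINNACLE® – PINNACLE® DM), the 2-sided 95% confidence interval for the difference", with a p-value. The section states that no formal hypothesis is attached and that the results serve clinical judgment. It names no covariate, stratum, matching or restriction.

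Appendix A lists the permitted shells. Under "PINNACLE Primary Cups" the surface headings run "POROCOAT GRIPTION DUOFIX POROCOAT GRIPTION DUOFIX POROCOAT GRIPTION POROCOAT", spread over the 100 Series, Sector, Multihole and 300 designs. The revision table adds "Standard Profile Deep Profile DPX", both in GRIPTION. Section 8.2 accepts that, because revisions are eligible, "variations in what is implanted will occur". It also has the sites record "details of the surgery and implants/components used".

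The only breakdown planned in section 11.9 is by surgical approach. The baseline summary in 11.11 does not name shell type or surface, although its list is left open.

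**The concern.** The endpoint is how far the shell moves in bone, so the surface that fixes the shell to bone is an obvious candidate for influencing it. The contrast carries only the label PINNACLE minus PINNACLE DM, and a reader will naturally take it as the contrast between standard and dual mobility constructs. If the two studies used different proportions of the three surfaces, the same number would also contain any difference between surfaces. The confidence interval would not reveal this, because it reflects sampling error only.

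Separating primary from revision hips would not remove the issue, since all three surfaces are permitted among the primary shells. At stake is what the sponsor can say about the dual mobility construct from the historical comparison, which is one of the two objectives in the synopsis. The single-arm mean, which is the primary endpoint, is not in question here.

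**Working it through.** **Inputs from the documents.** SD 0.2 mm, N = 30, two-sided 95% interval (section 11.8); permitted shells (Appendix A).

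**Inputs not in the documents, assumed here.** The n of DSJ_2018_02 (30 unless stated), its SD (0.2 mm), its shell mix, and any difference in migration between surfaces.

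**1. The plan's own figure.** 2 × 0.2/√30 = 0.073 mm. It reproduces. It is the margin for the single-arm mean, not for the difference from the historical study.

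**2. Count of permitted shells.** Primary: 100 Series 3 + Sector 3 + Multihole 2 + 300 1 = 9. Revision: 2. Total 9 + 2 = 11 design-by-surface combinations, from six designs and three surface names.

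**3. Half-width for the difference.** With 30 against 30, SE = 0.2 × √(1/30 + 1/30) = 0.0516 mm, and the t-based 95% half-width is 0.103 mm. With a historical n of 20 it is 0.116 mm; with 60 it is 0.089 mm.

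**4. Possible bias.** For two surfaces whose mean migration differs by d, used in shares p1 and p2 in the two studies, the unadjusted difference is shifted by (p1 − p2) × d.

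- Low end: 0.20 × 0.05 = 0.01 mm, about 10% of 0.103 mm.
- Middle: 0.40 × 0.10 = 0.04 mm, about 39%.
- High end: 0.60 × 0.20 = 0.12 mm, slightly more than the half-width. Here d equals one full anticipated SD.
- Equal mixes, or no surface effect: zero.

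**5. What that does to the reported p-value.** Assume no dual mobility effect and a 50-point mix difference. The chance of p < 0.05 comes from the noncentral t distribution with noncentrality bias/SE:

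| Surface effect d (mm) | Bias (mm) | Chance of p < 0.05, historical n = 30 | Range, historical n 20 to 60 |
|---|---|---|---|
| 0.05 | 0.025 | 8% | 7–9% |
| 0.10 | 0.05 | 16% | 14–20% |
| 0.20 | 0.10 | 48% | 40–60% |

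At a 25-point mix difference and d = 0.05 mm the bias is 0.0125 mm and the chance is about 6%.

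**6. Precision cost of stratifying by surface.** SE = SD/√Σ[n1k·n2k/(n1k + n2k)] over surfaces k, with margin 2 × SE, two surfaces and 30 per study:

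- Equal mixes: 0.103 mm, no loss.
- 25/75 against 50/50: the sum is 5 + 9 = 14, so the margin is 2 × 0.2/√14 = 0.107 mm.
- 75/25 against 25/75: the sum is 5.625 + 5.625 = 11.25, so the margin is 2 × 0.2/√11.25 = 0.119 mm.
- No surface in common: the sum is 0 and the stratified difference cannot be estimated.

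Restriction costs more. If it left 20 hips in each study (an assumption), the margin would be 2 × 0.2 × √(1/20 + 1/20) = 0.126 mm.

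**The case against.** A reader might infer that a coating difference will be reported as a dual mobility effect. The documents do not support that. Section 11.12.4 reports a mean difference without formal hypotheses, section 11.7 calls the intervals for the endpoint estimates exploratory, and nowhere is the difference attributed to the liner. Nor do the documents show that the shell mix of DSJ_2018_02 differs or that the surfaces behave differently. The three surfaces appear only as table headings, and the 6-week reference examination leaves earlier movement out of the main endpoint. The bias is therefore conditional on two unseen facts, and that part of the objection stands in full.

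A reader might also infer that an adjusted analysis should lead. That goes too far:

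- Eleven combinations cannot be modelled with about 30 hips, and Appendix A lists what may be implanted, not what will be.
- Both revision shells are GRIPTION only, so surface is partly tied to revision status and adjusting for surface alone would not isolate the construct.
- Section 8.2 shows that implant details are collected in this study. Nothing shows that they are available for the historical one.
- Primary/revision status and dislocation risk are unadjusted in the same way.

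Finally, section 11 describes itself as general and defers detail to a separate SAP, and the baseline list is open-ended. A shell table could still appear there, but no such commitment is in the documents as supplied.

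What survives is narrower. Calling a comparison exploratory does not remove confounding from the estimate, and clinical judgment is the very use that an unseen shell imbalance could mislead.

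**Conclusion.** The gap holds in a limited form. The documents permit three shell surfaces, measure shell migration against bone, and compare it with DSJ_2018_02 without any table, stratum or restriction that would show whether the shells were alike.

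Whether this biases the difference is unknown. The 0.01 to 0.12 mm range, against a half-width of about 0.103 mm, rests on assumed surface effects, assumed mix differences, an assumed historical n of 30 and an SD of 0.2 mm in both studies. It runs from negligible to material, so it shows that the question is worth checking, not that a bias exists. This is a cheap improvement to the historical comparison and not a flaw in the primary single-arm estimate.

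**What to change.** In section 11.12.4, or in the separate SAP before database lock:

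1. Keep the unadjusted comparison as planned.
2. Tabulate shell surface and primary/revision status for both studies.
3. Add one supportive comparison of Y translation at 2 years, stratified by surface or restricted to surfaces used in both studies, and within primary hips where numbers allow.
4. State in advance that, if surfaces do not overlap or the historical shell data cannot be obtained, the difference will be reported as not attributable to the dual mobility construct.

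For this study the change needs only SAP wording and implant data already recorded. For DSJ_2018_02 the sponsor must confirm that implant data by subject can be obtained. The downside is a somewhat wider interval (0.107 to 0.119 mm against 0.103 mm in the unequal-mix illustrations above) and a smaller n if the comparison is restricted.

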#### 11.13 Safety Endpoint Analysis

Adverse Events will be coded according to the Medical Dictionary for Regulatory Activities (MedDRA) version 21.1. Analyses will be conducted for all Subjects in the Safety Analysis Set.

An overall summary of the AE incidence will be presented and will include the number and percentage of Subjects having one or more:

- Serious adverse event (SAE)
- Device related AEs
- Procedure related AEs
- Withdrawals due to AE
- Deaths

The number (%) of Subjects with adverse events will be presented by MedDRA system organ class (SOC) and preferred term (PT) for all device related AEs, procedure related AEs and SAEs. A Subject-level listing will be provided to display details of all reported AEs.

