Sample Size	The purpose of this study is to summarize the mean subsidence (superior cup migration) of the acetabular shell as measured with RSA. Mean subsidence will be summarized at all time points; there are no hypotheses in this study. The standard deviation in observed migration values at 2 years post-op is anticipated to be approximately 0.2 mm. Based upon this standard deviation, a sample size of N=30 is anticipated to provide a 95% confidence interval for comparison with historical PINNACLE ® data with a margin of error of approximately $2(0.2/\sqrt{30}) = 0.073$ mm, which is deemed to be an adequate level of precision by the Sponsor. Up to 45 Subjects may be enrolled to offset pre and post-operative attrition.
Statistical Analysis	There are no formal hypothesis tests for this study. Summary statistics of primary, secondary and exploratory outcomes will be provided, along with 95% confidence intervals. Comparisons of the primary and secondary endpoints with historical PINNACLE ® data will be conducted using the t-test and the Fisher's exact test. Those comparisons will only be provided to facilitate clinical judgement.
Interim Analysis	An interim analysis will be conducted when all Subjects have reached 1-year post-op in order to give product development an understanding of acetabular cup subsidence that might be expected for future product development purposes and support regulatory submissions. There is no intention to utilize this interim analysis as a means to justify stopping the study early.
Determination if DMC/CEC	Not Required
Time and Events Schedule	See below

I         I         I>/>         I         I
> > >  >
> >
ļ
$\mathbf{i}$
>
C M/D
>
. >
· >

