#### 5.4 Safety Endpoints

The type and frequency of serious, non-serious, and device or procedure related Adverse Events across all study intervals will be summarized.

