#### 11.7 Levels of Significance

There are no specific hypotheses being tested in this study. To facilitate clinical interpretation, confidence intervals will accompany primary and secondary endpoint estimates and will be 2-sided 95% confidence intervals; these confidence intervals are considered to be exploratory.

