#### 11.10 Disposition of Study Subjects

An overall summary of the number of Subjects in each analysis set (Safety and Per Protocol) who had major protocol deviations, who withdrew before study completion, and who completed the study will be tabulated for all surgical approaches combined.

A patient accounting table to present the number of Subjects in the Safety Analysis Set at each visit interval will be summarized: theoretical due, deaths, withdrawn, and expected due in the interval.

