#### 11.12.3 Exploratory Endpoint Analysis

Exploratory analyses will include the following:

- Summaries of RSA measured subsidence at 6 Weeks, 3 months, 6 months and 1 year and 2 years will be conducted on the subset of Subjects where RSA data was obtained prior to discharge.
- Correlation of functional and health status outcomes (Harris Hip Score, HOOS Jr, and FJS-12) vs. RSA observations may be explored.
- Summaries of incidence of intraprosthetic dislocation
- Summaries of incidence of intraoperative complications

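### Adverse events are crude percentages of all operated subjects, which understates late events when subjects leave early; intraprosthetic dislocation has no named analysis set and no settled confidence interval

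*Combined protocol and SAP*

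**What the plan says.** **Adverse events.** Section 11.13 states: "An overall summary of the AE incidence will be presented and will include the number and percentage of Subjects having one or more" of a list covering serious, device-related and procedure-related events, withdrawals due to an event, and deaths. Counts and percentages by MedDRA class and term follow. On the denominator: "Analyses will be conducted for all Subjects in the Safety Analysis Set". Section 11.5 defines that set as every enrolled subject who undergoes THA, whatever the length of follow-up.

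**Follow-up.** Section 9.4 collects events from surgery until the subject's participation ends. Under 10.2, post-operative leavers are not replaced, except those who missed the 6-week visit because of COVID-19. Section 11.15 rules out imputation. On losses the synopsis says only: "Up to 45 Subjects may be enrolled to offset pre and post-operative attrition". No attrition rate is given.

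**IPD.** It is an exploratory endpoint. Section 11.12.3 offers "Summaries of incidence of intraprosthetic dislocation" and names neither analysis set nor denominator. The general convention in 11.9 for categorical variables is a count and percentage.

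**Intervals.** The synopsis says: "Summary statistics of primary, secondary and exploratory outcomes will be provided, along with 95% confidence intervals". Section 11.7 says only that "confidence intervals will accompany primary and secondary endpoint estimates", and 11.12.3 mentions no interval.

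**Timing.** Section 5.4 says that adverse events "across all study intervals will be summarized". Section 11.13 has no breakdown by interval. Section 11.10 does plan one for disposition: "A patient accounting table to present the number of Subjects in the Safety Analysis Set at each visit interval will be summarized", showing those due, dead and withdrawn.

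**The concern.** The percentage in 11.13 has a numerator limited to observed time and a denominator that assumes everyone was observed to 2 years. A subject who leaves at 3 months without an event contributes a full non-event. If the percentage is read as a 2-year incidence, it is too low for any event that can still occur after exit. Section 11.10 already tabulates the numbers needed to see this, but no event rate uses them.

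IPD and device-related events are direct clinical evidence on failure of this construct. IPD may well have a count of zero or close to it. Whether 0% is printed with or without an upper limit then decides how it is read, and the synopsis and Section 11 do not settle that.

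**Working it through.** **The plan's own figure.** The only sample-size figure is the margin of error for mean subsidence (11.8): 2 × 0.2/√30 = 0.073 mm. It reproduces, but says nothing about safety rates. The documents give no expected event rate, dropout rate or precision for safety, so the sizes below rest on assumptions, shown as ranges.

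**Inputs.** Follow-up T = 2 years (10.2). Denominator: all operated subjects (11.5, 11.13). Assumed: true 2-year incidence I from 2% to 20%; dropout d of 5%, 10%, 20% or 33%. The last is (45 − 30)/45, an upper reading of the enrolment reserve, because the synopsis says that the reserve also covers pre-operative losses.

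**Exits spread over time.** With constant event hazard λ = −ln(1 − I)/T and constant exit hazard μ = −ln(1 − d)/T, the expected crude proportion is

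λ/(λ + μ) × [1 − (1 − I)(1 − d)].

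For I = 5% and d = 20%: λ = 0.0256, μ = 0.1116, and 0.1869 × (1 − 0.95 × 0.80) = 0.1869 × 0.24 = 4.49%.

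**All exits at 6 weeks.** Expected crude proportion = (1 − d)I + d[1 − exp(−λ × 6/52)].

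| Dropout | Crude when I = 5%, exits spread | Relative shortfall, exits spread (I = 2% to 20%) | Relative shortfall, all exit at 6 weeks |
|---|---|---|---|
| 5% | 4.88% | about 2.5% | about 5% |
| 10% | 4.75% | about 5% | about 9% |
| 20% | 4.49% | about 10% | about 19% |
| 33% | 4.12% | 17% to 18% | about 31% |

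The worst case tried, 33% leaving at 6 weeks, turns a true 5% into 3.43%.

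**Early events.** If a share f of events falls in the first 6 weeks and exits are uniform afterwards, the relative shortfall is about d(1 − f)/2. With f = 0.9 and d = 1/3 this is 0.333 × 0.1/2 = 1.7%. For intraoperative events it is zero.

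**A concrete case.** Suppose 45 are operated, 15 leave at 1 year, and two have an event. The crude figure is 2/45 = 4.4% (exact 95% CI 0.5% to 15.1%). If both events come after the exits, the Kaplan-Meier estimate is 2/30 = 6.7%. If both come before, it is also 4.4%. The interval around the crude figure is much wider than the gap.

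**Zero IPD.** The exact two-sided 95% upper limit for 0/n is 1 − 0.025^(1/n): 11.6% at n = 30 and 7.9% at n = 45.

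**The case against.** Counts and percentages are a legitimate description in a study without hypotheses. The plan also offers help to a careful reader: every reported event is listed by subject (11.13), withdrawals and deaths are tabulated by interval (11.10), a subject whose study procedures stop because of an event is still followed for safety (10.1), and a more detailed SAP is announced (Section 11). The bias is small beside the sampling error. All of this stands, and it keeps the point modest. None of it yields a follow-up-adjusted rate.

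On intervals, 11.7 does not exclude exploratory endpoints and the synopsis expressly promises them. So omission is a risk of the wording, not a stated intention. The words in 5.4 can also mean pooled over all intervals.

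A reader might infer more than the documents support:

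- *Every implanted subject who leaves counts as event-free.* No. An event before exit is counted, including one that leads to a revision ending participation. A death without the event is a competing event, so treating it as a non-event is correct for cumulative incidence.
- *The plan divides IPD by everyone operated.* No section says so. A count and percentage is the fair reading of 11.9, but the set is unspecified.
- *The plan expects to lose a third of implanted subjects.* It states no rate.
- *The Fisher comparison will favour whichever study lost more subjects.* Section 11.12.4 covers primary, secondary and exploratory endpoints, not adverse events. Intraoperative complications do not depend on follow-up. IPD is reached only if DSJ_2018_02 has a counterpart, which the documents do not show.

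**Conclusion.** The point holds as a recommended improvement. Adverse events are crude percentages of all operated subjects, observation stops at exit, and nothing corrects for that. The 2-year incidence of events that can occur late is therefore understated whenever subjects leave event-free.

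Under a constant hazard with exits spread over follow-up, the relative shortfall is about 2.5% to 10% for dropout of 5% to 20%, and 17% to 18% at the upper reading of 33%. It is larger if exits cluster early, close to zero if events do, and absent if nobody leaves. The true size cannot be derived from the documents. It is minor beside sampling error at 30 to 45 subjects, but it runs in one direction and can be corrected.

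Two gaps for IPD need no assumed rate: the analysis set is not named, and the synopsis promises intervals that Section 11 does not carry through. It would be too strong to conclude that the safety results are invalid. The percentages remain a correct count of what was observed.

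**What to change.** In 11.12.3, 11.13 and the separate SAP, keep the counts and percentages and make four changes:

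1. Name the Safety Analysis Set as the set for IPD.
2. For IPD and device-related events, add the 2-year cumulative incidence with a 95% CI, from surgery to first event, censored at last contact, with death as a competing event (Aalen-Johansen; Kaplan-Meier suffices if there are no deaths). Plain Kaplan-Meier that censors deaths would overstate the incidence.
3. Show event counts by visit interval beside the number under follow-up from the 11.10 table, and say in 5.4 that this is what is meant.
4. Give exact (Clopper-Pearson) 95% limits for IPD and intraoperative complications, and align 11.7 with the synopsis. With no IPD events the cumulative incidence estimate supplies no useful interval, so give the exact limit both for all operated subjects and for those followed to 2 years. Intraoperative complications need no follow-up adjustment.

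The cost is SAP wording and a few table columns. No new data collection appears necessary, since 12.7 already asks source documents to record the dates of adverse events and subject status. The price is wide intervals and slightly less favourable figures.
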